4.0 PARTICIPANT REGISTRATION/PROCEDURES

The following information is to be provided at the time of registration to the trial:

Participant Identification Information for PATCH 2 & PATCH 3:

- Participant initials (first and last)
- Participant's chronic medical problems
- Gender
- Birth date (mm/yyyy)
- Race
- Ethnicity
- Nine-digit ZIP code
- State of residence
- County of residence
- Cell phone number and alternate numbers
- Email address

Participant Identification Information for PATCH 2 Only (Sub-study 1): Identify the number of fulltime inhabitants at the residence where the participant will stay during the 14-day self-quarantine as well as ages and sex of each co-inhabitant and relationship to the study participant.

Participant Procedure for PATCH 2 (Sub-Study 1) (See study process flows)

1. Interested participants self-refer for study by completing online eligibility checklist on study portal (www.patchstudy.com)
2. Review inclusion and exclusion criteria: participant is 50-75 years of age and self-reported as having a fever within the last four days will undergo swab testing for COVID-19 per clinical care guidelines and approach, and then sent home for a self-imposed quarantine
3. Reviews the study and the Informed Consent Form with the subject and obtains informed consent via DocuSign
4. Participant study ID is assigned, and subsequently, randomized into a study arm (HCQ or placebo).
5. Package containing blinded study drug, study journals (medicine log, symptom tracker and experience log) and study documents (details on aims, design, consent forms, and any additional instructions) delivered to address provided by participant as place of residence during period of self-quarantine. Day 1 is defined as the first day the blinded study drug is taken by the participant
6. Lab provides participant's COVID-19 test results to designated Co-PI with designee
7. PI or designee calls participant informing them of result, discussing how to proceed on the trial (if positive, continue taking medication; otherwise, stop) and documenting discussion.
8. Each day, participants will record 1) temperature (to be reported twice daily, either via thermometer or self-report); 2) time medication taken; 3) any symptoms and AEs; and 4) if any co-inhabitants develop symptoms and/or become positive for COVID-19 (confirmed by accepted testing methods)
9. Three times a week, participants will be called by clinical research coordinators to assess AEs and symptoms with all discussions well-documented. Clinical research coordinators may clinically escalate any medical determinations to Co-PI
10. After Day 14, which marks the end of the treatment period, participants will no longer be expected to continue self-reporting information into the study portal. Participant will undergo follow-up testing for COVID-19 at two additional time points. The first will be either day 15, 16 or 17, with the second on either on day 29, 30 or 31
11. If during active participation, the participant reports worsening of symptoms related to COVID-19 from baseline, this is reported to the PI for further clinical evaluation

Participant Procedure PATCH 3 (Sub-Study 2) (See study process flows)

1. Interested participants self-refer for study by completing online eligibility checklist on study portal (www.patchstudy.com)
2. Review inclusion and exclusion criteria:
 - Currently employed as a health care worker ([name]; Doctor of Osteopathic Medicine, DO; Nurse Practitioner, NP; Physician's Assistant, PA; and [name] or other members of the medical care team with significant COVID-19 exposure);
 - Asymptomatic and presumed negative for COVID-19 (no confirmatory testing conducted);
 - Scheduled for an average of >20 hours per week of clinical care over the next two months (or equivalent indicating at least part-time employment).
 - Willing to comply with their employer's potential or confirmed COVID-19 incident protocol
 - Agrees to undergo COVID-19 testing per standard of care using an FDA approved method upon the presentation of symptoms indicative of an influenza like illness (if a confirmatory COVID-19 diagnosis is given, participant will be offered to cross-over to HCQ 600 mg qd for 14 days.)
3. Reviews the study and the Informed Consent Form with the subject and obtains informed consent via DocuSign
4. Participant study ID is assigned, and subsequently, randomized into a study arm (HCQ or placebo).

PATCH 2 & 3 TRIAL

5. Package containing blinded study drug supply, study journals (medicine log, symptom tracker and experience log) and study documents (details on aims, design, consent forms, and any additional instructions) are delivered to the address provided by participant as place of residence during study. Delivery of blind study drug supply will occur in two shipments, each containing a 30-day supply. Day 1 is defined as the first day the blinded study drug is taken by the participant.
6. Each day active medication is taken (HCQ or placebo), participants will record 1) temperature (to be reported twice daily, either via thermometer or self-report); 2) time medication taken; and 3) any symptoms and AEs.
7. Every week, clinical research coordinators will review the study portal to assess for AEs and indication of reported symptoms indicative of influenza like illness. The research coordinator will also review self-reported fever and/or temperature. If COVID-19 symptoms are evident, the research coordinator will outreach to the HCW (at clinic or by phone). Clinical research coordinators may clinically escalate any medical determinations to Co-PI following study portal review.
8. The HCW also has access to the study coordinators via the study phone number. If the HCW feels symptomatic, then he/she should call the clinical research coordinator team, and document symptoms in the study portal. Clinical research coordinators may clinically escalate any medical determinations to Co-PI.
9. If during the study symptoms indicative of an influenza like illness present, participant will be asked to comply with their employer's potential or confirmed COVID-19 incident protocol and be tested for COVID-19 by an accepted method. Participants negative for COVID-19 continue with the assigned blinded study drug regimen.
10. If confirmed COVID-19 diagnosis, participant will be unblinded. Participants assigned to HCQ can continue with medication schedule. Individuals assigned to the placebo arm will be offered the opportunity to cross-over to HCQ 600 mg daily for 14 days. Individuals will be expected to continue self-reporting temperature, time medication taken and any symptoms/AEs into the study portal while taking active HCQ medication.
11. Participants who remain undiagnosed for COVID-19 by the end of the medication period (Day 60) will be asked to undergo COVID-19 and serology testing for IgM/IgG on either Day 61, 62, or 63.

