1.2 Secondary Objectives

PATCH 2 (Sub-Study 1): Rate of secondary infections for co-inhabitants, rate of adverse events (AEs), and rate of COVID-19 negativity (confirmed by accepted testing methods) after 14 days of treatment

PATCH 3 (Sub-Study 2): Number of shifts missed, rate of hospitalization, and rate of adverse events (AEs)

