8.4 Participant Safety Monitoring and Data Collection

Adverse events will be captured via self-report by participants within the study portal. Participants are instructed to contact the study team at the phone number provided in the Welcome Packet to report all adverse events. The study team will reach out to the participant to gather additional information surrounding the adverse event in order to complete DAIDS grading if necessary. Additional information pertaining to the adverse event will be captured within the study portal by the study team and reviewed by the PI's for causality to study drug. Adverse events meeting seriousness criteria will be reported to the IRB as noted below.

PATCH 2 (Sub-Study 1):

Clinical Symptom Monitoring: Participants will be contacted three times per week to assess AEs and COVID-19 symptoms and collect/review self-reported AE's. Worsening COVID symptoms and/or new or worsening AE's will be reviewed by the PI's for causality to study drug.

Temperature Measurements: Home quarantined participants will be asked to report twice daily either presence of fever or temperature and record the measurements.

COVID-19/SARS-CoV-2 Testing: On Days 15-17 and 29-31, participants will undergo follow-up testing for COVID-19.

Pill Count and Journal: Participants will be contacted three times per week and following the end of treatment to compare data entry on the portal and collect any missed entries over the phone.

Monitoring Co-Inhabitants: Participants will be contacted three times per week to identify if any co-inhabitants have developed symptoms and/or tested positive for COVID-19. Participants will also be asked to provide a description of co-inhabitants' symptomology, and time of positive testing for COVID-19 via self-reporting.

PATCH 3 (Sub-Study 2):

Adverse events will be captured solely based on participant self-reporting via the study portal and/or by calling the study team at the number provided in the Welcome Packet. The study team will review the portal for self-reported AE's not previously reported to the study team. New AEs not previously reviewed which cannot be

PATCH 2 & 3 TRIAL

graded based upon self-reported data within the portal will require follow-up from the study team to gather additional information from the participant. New or worsening AE's will be reviewed by the PI's for causality to study drug.

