PATCH 3 (Sub-Study 2), Prophylaxis in Health Care Workers: The transmission of SARS-COV-2 from patient to hospital worker depends on many factors including specifics of standard care to prevent transmission, but especially on the number of patients seen at a given hospital or outpatient practice. Across China the reported hospital worker infection rate is 3.8%, but in Wuhan it is reported as 58% at the height of the epidemic. We will use a 10% transmission rate as the null hypothesis (low dose group). In order for HCQ to be considered effective our alternative hypothesis will be a 1% transmission rate. With a 1:1 randomization for the HCQ to control arms we would require a total of 350 health care workers across all participating ProHealth NY and AHN sites. With the placebo group of 175 participants and the high dose HCQ arm of 175 participants, a one-sided z-test ($\alpha=0.05$) comparing the rates in the two groups would have an at least 80% power to detect a significant difference when the difference in the population rates is at least 9%.

The *hypothesis* will be tested using a one-sided test, with a z-score corresponds to the log of the odds-ratio for the rate of transmission between the two groups. We will obtain the estimate of the odds ratio, and 95% CI, from logistic regression.

Interim analysis: We will perform two interim analyses at 25% and 50% completion, testing for early efficacy or futility, using z-score boundaries that follow Hwang-Shih-DeCani alpha spending rules. Following those rules, we have 80% power using 100% of the sample, if our 10% versus 1% scenario is true.

Z-Value Boundaries

Stage	Boundaries		Information Proportion
	Efficacy	Futility	
1	2.9473	-1.2318	0.2500
2	2.5825	-0.2676	0.5000
3	1.6664	1.6664	1.0000

P-Value Boundaries

Stage	Boundaries		Information Proportion
	Efficacy	Futility	
1	0.00160	0.89099	0.2500
2	0.00491	0.60550	0.5000
3	0.04782	0.04782	1.0000

16.2 Analysis of Secondary Endpoints.

Secondary outcomes will be analyzed as summary statistics, with group means, odds-ratios, and 95% CIs. We may conduct exploratory analyses using regression methods appropriate for each type of measure. Tests for significance of estimated parameters will not be reported as we will not be controlling for multiple testing.

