PATCH 2 (Sub-Study 1): Rate of secondary infection of housemates is a binomial count by household. We will summarize the proportion or rate by group, with 95% CI. With sufficient data, we will explore subgroups, patient, and secondary patient characteristics using logistic regression. Rate of hospitalization is a binary measure. We will summarize rates by group and estimate the odds-ratio for treatment. Adverse event rates will be summarized as a count by participant, and mean count by group, and we will estimate a rate-ratio for treatment. We will summarize rates by group and estimate the odds-ratio for treatment.

PATCH 3 (Sub-Study 2): Rate of hospitalization is a binary measure. We will summarize rates by group and estimate the odds-ratio for treatment. Adverse event rates will be summarized as a count by participant, and mean count by group, and we will estimate a rate-ratio for treatment. We will summarize the count of shifts missed by group and estimate the rate ratio for treatment.

REFERENCES

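### PATCH 2 does not record co-inhabitants' illness or test status at registration and defines no secondary case, so infections present before Day 1 can enter the household endpoint and pull it toward no effect

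*Combined protocol and SAP*

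**What the plan says.** Protocol section 1.2 lists "Rate of secondary infections for co-inhabitants" among the PATCH 2 secondary objectives.

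- **Registration (section 4.0).** For the household, the plan takes the number of full-time residents and the "ages and sex of each co-inhabitant and relationship to the study participant". It asks for no symptoms, onset date or earlier test result.
- **Daily log (section 4.0, PATCH 2 procedure, step 8).** The participant records "if any co-inhabitants develop symptoms and/or become positive for COVID-19 (confirmed by accepted testing methods").
- **Calls three times a week (section 8.4).** Staff ask the participant to "identify if any co-inhabitants have developed symptoms and/or tested positive for COVID-19", and collect a description of symptoms and the "time of positive testing for COVID-19 via self-reporting". No date of symptom onset is named.
- **Analysis (section 16.2).** "Rate of secondary infection of housemates is a binomial count by household". The plan adds: "We will summarize the proportion or rate by group, with 95% CI". It gives no case definition, at-risk denominator or start date, and no rule for infections present before treatment. For all secondary outcomes, "Tests for significance of estimated parameters will not be reported as we will not be controlling for multiple testing".

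**The concern.** Treating the index patient can only prevent transmission that happens after treatment starts. The index patient qualifies by reporting a fever in the four days before enrolment (section 3.1), which does not limit how long ago the illness began. Day 1 is the first dose, taken once the package has reached the home. Section 2.1 itself describes household transmission as high. Some housemates may therefore be infected before Day 1, and some may be the source of the index case.

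Such infections cannot respond to the index patient's treatment. If they are counted, randomization spreads them equally over the arms in expectation, and the estimated effect moves toward none. An analyst could not repair this later, because status at baseline and date of onset would not be in the data.

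**Working it through.** The plan states no rate, effect size, sample size or power for this endpoint, so there is no figure of its own to reproduce. The check has two parts.

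**1. Which prior infections can the planned data identify?**

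| Housemate's status before Day 1 | What the planned data show | Separable? |
|---|---|---|
| Tested positive before Day 1 | Time of positive test (section 8.4); also not a new event under the daily log | Yes, though no analysis rule uses it |
| Ill before Day 1, first tested after | A positive test during follow-up; no onset date | No |
| Incubating or without symptoms at Day 1, tested after | A positive test during follow-up | No, and baseline questions would not catch it either |

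The protocol schedules no testing of co-inhabitants, so the date of a positive test can lag the infection.

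**2. How much dilution could follow?**

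All inputs here are assumptions, since the documents give none of them:

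- p = true risk after Day 1 among housemates not yet infected: 20% on placebo, 10% on HCQ, so the true risk ratio (RR) is 0.50 and the true risk difference (RD) is 10 points.
- q = share of housemates already infected at Day 1, equal in both arms.

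If every prior infection is counted, observed risk = q + (1 − q)p:

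| q | Placebo | HCQ | RR | RD |
|---|---|---|---|---|
| 10% | 0.10 + 0.90 × 0.20 = 0.28 | 0.10 + 0.90 × 0.10 = 0.19 | 0.68 | 9 points |
| 20% | 0.20 + 0.80 × 0.20 = 0.36 | 0.20 + 0.80 × 0.10 = 0.28 | 0.78 | 8 points |
| 30% | 0.30 + 0.70 × 0.20 = 0.44 | 0.30 + 0.70 × 0.10 = 0.37 | 0.84 | 7 points |

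If half of the prior infections are identified and removed:

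- q = 10%: RR = (0.05 + 0.09) / (0.05 + 0.18) = 0.14 / 0.23 = 0.61.
- q = 20%: RR = (0.10 + 0.08) / (0.10 + 0.16) = 0.18 / 0.26 = 0.69.

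If none is counted, RR is 0.50. At q = 10% with those housemates left in the denominator, the risks are 0.90 × 0.20 = 18% and 0.90 × 0.10 = 9%. The ratio is intact, but the rates are understated and RD is 9 points. This is why the denominator needs a rule as well as the numerator.

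For other assumed values, with all prior infections counted:

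- True RR 0.50, placebo risk 10% to 30%, q 5% to 30%: observed RR runs from 0.1925 / 0.335 = 0.575 (placebo risk 30%, q = 5%) to 0.335 / 0.37 = 0.905 (placebo risk 10%, q = 30%).
- True RR 0.70, placebo risk 20%, q 5% to 30%: observed RR runs from 0.183 / 0.24 = 0.763 to 0.398 / 0.44 = 0.905.

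**The case against.** A reader might infer that the plan counts infections predating treatment as secondary infections, and that the data needed to remove them are never collected. The documents support neither reading. The daily log is worded for new events: housemates who *develop* symptoms or *become* positive. Section 8.4 collects the time of a positive test, so a positive before Day 1 can be set aside. The process-flow charts in Appendix 1 were not readable in the copy reviewed, so a field that appears only there cannot be ruled out.

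Further points on the other side:

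- The ratios of 0.68 to 0.84 are the case in which every prior infection is counted. The study does not test housemates, so a prior infection enters only if the housemate happens to be tested or noticed after Day 1 and the participant reports it.
- The delay before treatment may be short, since the PATCH 2 job aid (Appendix 3) describes an overnight courier package.
- The bias is toward no effect and cannot be expected to create a false benefit. No boundary or sample size depends on this endpoint.

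All of this stands, and it sets the scale of the point. It does not remove the gap. A housemate ill at registration and first tested after Day 1 satisfies the wording of the log, carries a test date inside follow-up, and is met by no analysis rule. An overnight delivery does not shorten the exposure that came before enrolment.

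**Conclusion.** The point holds in a limited form. Infections present before Day 1 *can* be counted as secondary infections, because baseline status is not recorded and neither a secondary case nor an at-risk denominator is defined. The planned data separate housemates who tested positive before Day 1, but not those already ill and first tested afterwards.

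The direction is toward no effect, given that prior infections are equally common in the arms and equally likely to be reported. The size cannot be stated from the documents. The ratios above rest on assumed attack rates and an assumed share already infected, and should be read as illustrations from no dilution (0.50) upward, not as the expected loss.

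Severity is low: the endpoint is secondary and descriptive. An estimate with a 95% confidence interval will still be reported, and it is that estimate which could be diluted.

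**What to change.** 1. **Registration form.** For each co-inhabitant, record current COVID-19 symptoms with date of onset, and any earlier positive test with its date. Ask for onset date in the existing follow-up calls too, so that illness beginning between registration and Day 1 can be placed.
2. **Section 16.2.** Define the at-risk denominator and a secondary case by onset or test date relative to Day 1. Exclude from numerator and denominator any housemate symptomatic or positive before Day 1.
3. **Sensitivity analysis.** Repeat the summary without cases whose onset falls in the first days after Day 1, because the baseline items do not catch infections still incubating. The documents give no basis for the number of days, so it should be fixed before unblinding. This stays a sensitivity analysis because the dropped cases arise after treatment has started.

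The cost is a few form fields, one added question in calls already planned, and a short addition to the analysis text. Fewer housemates will be analysed, some uninfected housemates with other illnesses will be excluded, and some dilution from incubating or symptom-free infections will remain. The baseline items need to be in place before households are registered, since onset dates recalled later are less reliable.

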3. Immunosuppressive medications, including, corticosteroids at doses exceeding 10mg/day of prednisone or equivalent, methotrexate, azathioprine, and TNF-alpha blockers. Use of immunosuppressive medication for the management of study treatment-related AEs or in subjects with contrast allergies is acceptable. In addition, use of topical, inhaled and intranasal corticosteroids is permitted
4. Live attenuated vaccines during the study through 180 days after the last dose of both drugs

7.3 Duration of Protocol Treatment and Follow-up.

PATCH 2 (Sub-Study 1) duration of treatment is 14 days (two weeks) with follow-up with COVID-19 testing on Day 15, 16 or 17, and Day 29, 30 or 31 where Day 1 marks the first day blinded study drug is taken by the participant.

PATCH 3 (Sub-Study 2) duration of treatment is up to 60 days with an option to cross-over for participants taking placebo upon presentation of symptoms indicative of an influenza like illness and testing positive for COVID-19 (or a COVID-19 diagnosis is made by a health care provider). Participants remaining undiagnosed for COVID-19 by Day 60 will undergo testing for SARS-CoV-2 and IgM/IgG antibodies on either Day 61, 62, or 63. The maximum study medication duration and follow-up testing is 63 days.

7.4 Crossover from Control to HCQ arm.

PATCH 2 (Sub-Study 1): There is no cross-over.

PATCH 3 (Sub-Study 2): Participants that develop symptoms indicative of an influenza like illness and diagnosed with COVID-19 will be unblinded. If they were assigned to the placebo arm and deemed appropriate, they will be offered the option crossover to HCQ 600 mg qd for 14 days.

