9.2 Adverse Events Reporting Period

The study period during which adverse events must be reported is defined as the period from the initiation of the first study treatment to the last administration of study treatment.

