10.0 SERIOUS ADVERSE EVENTS

A serious adverse event is any AE that is:

- fatal
- life-threatening
- requires or prolongs hospital stay
- results in persistent or significant disability or incapacity
- a congenital anomaly or birth defect
- a suspected transmission of an infectious agent (e.g., pathogenic or nonpathogenic) via the study drug
- an important medical event
- All Serious Adverse Events (SAEs) that occur following the participant’s written consent to participate in the study must be reported, whether related or not related to study drug. If applicable, SAEs must be collected that relate to any later protocol-specified procedure.
- Following the participant’s written consent to participate in the study, all SAEs, whether related or not related to study drug, are collected, including those thought to be associated with protocol-specified procedures. The investigator should report any SAE occurring after these aforementioned time periods, which is believed to be related to study drug or protocol-specified procedure.
- An SAE report should be completed for any event where doubt exists regarding its seriousness;
- If the investigator believes that an SAE is not related to study drug but is potentially related to the conditions of the study (such as withdrawal of previous therapy or a complication of a study procedure), the relationship should be specified in the narrative section of the SAE Report Form.

All SAEs should be followed to resolution or stabilization. Serious adverse events that are ongoing at the end of the study period must be followed to determine the outcome. Any serious adverse event that occurs after the study period and is at least possibly related to the study treatment or study participation should be recorded and reported immediately to the Medical Monitor and the IRB per the IRB reporting guidelines.

PATCH 2 & 3 TRIAL

All adverse events that do not meet any of the criteria for serious should be regarded as non-serious adverse events.

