10.2 Hospitalization, Prolonged Hospitalization or Surgery

Any adverse event that results in hospitalization or prolonged hospitalization should be documented and reported as a serious adverse event unless specifically instructed otherwise in this protocol. Any condition responsible for surgery should be documented as an adverse event if the condition meets the criteria for an adverse event.

Neither the condition, hospitalization, prolonged hospitalization, nor surgery are reported as an adverse event in the following circumstances:

- Hospitalization or prolonged hospitalization for diagnostic or elective surgical procedures for a preexisting condition. Surgery should not be reported as an outcome of an adverse event if the purpose of the surgery was elective or diagnostic and the outcome was uneventful.
- Hospitalization or prolonged hospitalization required to allow efficacy measurement for the study.
- Hospitalization or prolonged hospitalization for therapy of the target disease of the study, unless it is a worsening or increase in frequency of hospital admissions as judged by the clinical investigator.

Expected adverse events are those adverse events that are listed or characterized in the Package Insert or current Investigator Brochure.

Unexpected adverse events are those not listed in the Package Insert (P.I.) or current Investigator Brochure (I.B.) or not identified. This includes adverse events for which the specificity or severity is not consistent with the description in the P.I. or I.B. For example, under this definition, hepatic necrosis would be unexpected if the P.I. or I.B. only referred to elevated hepatic enzymes or hepatitis.

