15.2 Response Criteria

PATCH 2 (Sub-Study 1): Measurement of SARS-CoV-2 positivity confirmed by an accepted testing method. Rate of hospitalization will be defined by a hospitalization occurring within 30 days of the date of participant enrollment.

PATCH 3 (Sub-Study 2): Rate of COVID-19 infection will be defined by measurement of SARS-CoV-2 identified by accepted testing methods.

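### PATCH 2's primary endpoint counts hospitalisations to 30 days from enrolment, but no readable rule collects them to day 30 and the reporting rules conflict after Day 14

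*Combined protocol and SAP*

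**What the plan says.** The endpoint is set in section 15.2: "Rate of hospitalization will be defined by a hospitalization occurring within 30 days of the date of participant enrollment". Collection is described in several other places.

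- **Portal.** Section 4.0, PATCH 2 item 10: after Day 14 "participants will no longer be expected to continue self-reporting information into the study portal". Day 1 is the first day drug is taken, not the day of enrolment.
- **Adverse event period.** Section 9.2: "from the initiation of the first study treatment to the last administration of study treatment". On the 14-day course in section 7.3 this ends at Day 14, or sooner if drug is stopped early.
- **Serious events.** Section 10.0 says that after consent "all SAEs, whether related or not related to study drug, are collected", and gives no end date. Sections 9.4 and 10.0 also say that a serious event after the study period is to be reported if it is at least possibly related to treatment or participation.
- **Exemption.** Section 10.2 lists circumstances not reported as an adverse event, among them "Hospitalization or prolonged hospitalization for therapy of the target disease of the study, unless it is a worsening" or an increase in the frequency of admissions, as the clinical investigator judges.
- **Later contacts.** Sections 4.0 and 8.4 schedule COVID-19 tests at Days 15-17 and 29-31. Section 8.4 adds a contact after treatment to reconcile journal entries. None is said to ask about admission.
- **Removal.** Section 12.0 takes participants off study when progressive disease is documented, and does not say that outcome collection continues.

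**The concern.** The endpoint clock and the reporting clocks do not match. The endpoint runs for 30 days from enrolment. Routine reporting runs from first dose to Day 14. After that, whether an admission reaches the database depends on which section a site follows and on two judgements: whether the event is possibly related, and whether it is a worsening. The event most exposed to those judgements, a COVID-19 admission, is the primary event.

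The primary test rests on about 100 COVID-19-positive patients and, under the planning rates, about 17.5 expected admissions (15 + 2.5), so a few missed events matter. Equal loss in both arms shrinks the difference and the power. Unequal loss, for instance if drug changes when patients are admitted, can bias the comparison. No analysis can recover an admission that nobody recorded.

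**Working it through.** **1. The two clocks.** Let L be the days from enrolment to first dose. The documents do not give L; assume 0 to 3. Day 14 falls L + 13 days after enrolment, so the part of the window left after required portal entries is 30 − (L + 13) = 17 − L days: 17, 16, 15 or 14 of the 30. Day 29, the earliest permitted last test, falls L + 28 days after enrolment: 28, 29, 30 or 31. With L of 0 or 1 the last contact can come before the endpoint window closes.

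**2. Which stated rule would record an admission on, say, Day 20?**

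| Section | Records it? |
|---|---|
| 4.0 item 10, portal | Not required |
| 9.2, adverse event period | Outside the period |
| 10.0, all SAEs after consent | Yes, no end date |
| 9.4 and 10.0, after the study period | Required if at least possibly related |
| 10.2, target-disease exemption | Exempt unless judged a worsening or an increase in frequency |
| 9.4, assessment at each contact | Possibly, at the Day 29-31 contact |
| 4.0 and 8.4, calls three times a week | No stated end; content is AEs, symptoms, journal and co-inhabitants |
| 12.0, removal on progression | May end contact first |

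The rules give different answers, and none names admission status as an item to collect to day 30.

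**3. The plan's power.** Inputs from section 16.1: 30% vs 5% hospitalised (70% vs 95% not hospitalised), 50 per arm, one-sided alpha 0.05. Mean rate = 0.175.

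- Null standard error = √(2 × 0.175 × 0.825 / 50) = 0.0760
- Alternative standard error = √((0.30 × 0.70 + 0.05 × 0.95) / 50) = 0.0718
- Power = Φ((0.25 − 1.645 × 0.0760) / 0.0718) = 95.9%

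The stated figure of at least 90% is met.

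**4. Equal loss.** If a share m of admissions goes unrecorded in both arms, the recorded rates are 0.30(1 − m) and 0.05(1 − m). The share m is assumed. Power below is by exact binomial enumeration at 50 per arm, using only the final efficacy boundary z = 1.6813. The two tests are the pooled score z and the log-odds-ratio z = ln(ad/bc) / √(1/a + 1/b + 1/c + 1/d), with 0.5 added to each cell.

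| m | Recorded rates | Difference | Power, score / log-OR |
|---|---|---|---|
| 0 | 30.0 vs 5.0% | 25.0 points | 97.0 / 96.2% |
| 10% | 27.0 vs 4.5% | 22.5 points | 95.2 / 93.9% |
| 20% | 24.0 vs 4.0% | 20.0 points | 92.6 / 90.3% |
| 30% | 21.0 vs 3.5% | 17.5 points | 89.0 / 84.9% |

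Simulating all three looks with the stated boundaries gives nearly the same: 96.8/96.1% at no loss, 92.3/90.0% at 20% and 88.6/84.7% at 30%.

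**5. Unequal loss.** Take a true 20% rate in both arms and the stated boundaries (simulation, score z). Missing 10% of placebo and 30% of HCQ admissions gives a one-sided error of about 13% instead of 5%. Reversing the shares gives about 1.5%. This shows direction only; nothing in the documents says which arm would lose more.

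**The case against.** The strongest reply is that the plan already has routes to these events. Section 10.0 makes an event requiring a hospital stay serious and collects all such events from consent, which also covers the days before first dose. Section 9.4 has staff assess adverse events at each contact, which on its face reaches Days 15-17 and 29-31. Section 15.1 keeps participants evaluable for toxicity through final assessment. The PATCH 2 Job Aid asks for daily uploads for the whole study. The exemption in 10.2 leaves out a worsening, and patients enrolled as not needing hospital would often meet that exception. Finally, section 14.0 hands the schedule of events to process flows whose figures are not shown.

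Most of this stands, and it limits the point. It does not remove it: 10.0 conflicts with 9.2 and with the relatedness limit, the Job Aid conflicts with 4.0 item 10, and the exception in 10.2 is decided case by case.

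Three stronger readings are tempting and not supported:

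- **That a patient admitted on Day 20 is scored as not hospitalised.** Section 15.2 counts that patient, and there are routes by which a site could learn of the admission. It may be missed; it is not defined away.
- **That housemate infections after Day 14 are lost.** No window after Day 14 is defined for that outcome, and the calls about co-inhabitants have no stated end.
- **That false efficacy of 15 to 42% should be expected.** That range comes from true rates of 30% in both arms, HCQ moving 30 to 50% of its admissions past Day 14 against 10% on placebo, and none of those being captured. The documents support neither the delay pattern nor total loss.

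**Conclusion.** The point holds as a gap and a conflict in how the primary endpoint is ascertained. Roughly half of the 30-day window (14 to 17 days, with first dose assumed 0 to 3 days after enrolment) lies after required portal reporting ends, and the readable text does not guarantee that admissions in that period are recorded.

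The effect cannot be sized from the documents, because the share of admissions after Day 14 and the share of those missed are both unknown. Under equal loss the stated 90% power survives up to about 20% of events lost and fails at 30% (89.0/84.9%). Unequal loss could move type I error either way. If the process flows or case report forms that cannot be seen already contain an admission question to day 30, what remains is to reconcile the written sections.

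**What to change.** - **Sections 4.0 item 10 and 8.4.** Record admission status and date at the existing Day 15-17 and Day 29-31 contacts. Place the last one no earlier than 30 days after enrolment. If a swab is missed, phone the participant or the alternate number already taken at registration.
- **Coverage.** Do this for every randomised participant, whether or not drug was stopped or the participant was removed under section 12.0.
- **Section 10.2.** State that the target-disease exemption affects adverse event reporting only, and that every admission from enrolment to day 30 is entered as an endpoint event.
- **Sections 9.2, 9.4 and 10.0.** Reconcile the period and the relatedness condition for serious events, and align the Job Aid's upload instruction with 4.0 item 10.

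The cost is protocol wording, one short question at two contacts that already exist, and some phone calls. No visit or test is added, and treatment does not change.
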